9.4 Safety and Tolerability Assessments

9.4.1 Adverse events

Where changes in severity are recorded in the Case Report Form (CRF), each separate severity of the AE will be reported in the listings, only the most severe will be used in the summary tables. A pre-existing condition is defined as an AE that starts before the subject has provided written informed consent and is ongoing at consent. A non-treatment emergent AE is defined as an AE which starts after informed consent but prior to dosing. A treatment-emergent AE is defined as an AE which occurs postdose or which is present prior to dosing and becomes more severe postdose.

The summary and frequency AE tables will be presented for all causalities and those considered related to the study drug. All AEs will be listed.

Treatment-emergent AEs will be summarized by treatment (including overall lasmiditan treatment periods and overall placebo treatment period), severity and relationship to the study drug, in separate outputs, split by population, as well as sex within population. Hence the following summary tables will be created:

- Summary of Treatment-Emergent AE (All Causalities) by Population
- Summary of Treatment-Emergent AE (Related to Study Treatment) by Population
- Summary of Treatment-Emergent AE (All Causalities) by Sex Within Population
- Summary of Treatment-Emergent AE (Related to Study Treatment) by Sex Within Population

The frequency (the number of AEs, the number of subjects experiencing an AE and the percentage of subjects experiencing an AE) of treatment-emergent AEs will be summarized by treatment (including overall lasmiditan treatment periods and overall placebo treatment periods), Medical Dictionary for Regulatory Activities (MedDRA) version 21.0 system organ class and preferred term, and split by population, as well as sex within population, in separate outputs. Any serious AEs will be tabulated. Hence the following frequency tables will be created:

- Frequency of Subjects with Treatment-Emergent AE (All Causalities) by Population
- Frequency of Subjects with Treatment-Emergent AE (Related to Study Treatment) by Population
- Frequency of Subjects with Treatment-Emergent AE (All Causalities) by Sex Within Population
- Frequency of Subjects with Treatment-Emergent AE (Related to Study Treatment) by Sex Within Population

Similar outputs but sorting by preferred term, instead of by system organ class and preferred term, will be created. Hence the following summary tables will be created:

- Summary of Treatment-Emergent AE (All Causalities) by Population and Treatment in Order of Frequency
- Summary of Treatment-Emergent AE (Related to Study Treatment) by Population and Treatment in Order of Frequency
- Summary of Treatment-Emergent AE (All Causalities) by Treatment and Sex Within Population in Order of Frequency
- Summary of Treatment-Emergent AE (Related to Study Treatment) by Treatment and Sex Within Population in Order of Frequency

Subject numbers for all TEAEs will be listed. Pre-existing conditions for individual subjects will also be listed.

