#### 3.1. Study Rationale

Lasmiditan is a highly selective and potent agonist of the 5-hydroxytryptamine (5-HT)1F receptor that is being developed as a neurally acting treatment for migraine.

This study is the first clinical evaluation of lasmiditan in Japanese subjects, and will facilitate subsequent clinical trials in Japanese patients. Characterization of the safety and pharmacokinetics (PK) of lasmiditan in Japanese subjects is essential for further clinical development in Japan. Additionally, as the majority of migraine patients are female, and previous studies suggest a higher exposure in female subjects, the safety and PK in female Japanese subjects will also be explored. Caucasian subjects are included to explore the differences in safety, tolerability, and PK of lasmiditan between Japanese and Caucasian subjects.

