**Table LAIE.4.1. Objectives and Endpoints**

Objectives	Endpoints
Primary  To explore the safety and tolerability of single and repeated oral doses of lasmiditan in healthy Japanese subjects, and single oral doses of lasmiditan in healthy Caucasian subjects.	Incidence of TEAEs and SAEs.
Secondary  To evaluate the PK of lasmiditan in healthy Japanese and Caucasian subjects.	AUC(0-∞), C max , and t max .
Exploratory  To evaluate the PK of metabolites M7, M8, (S,R)-M18, and (S,S)-M18 in healthy Japanese and Caucasian subjects.  To explore the safety, tolerability, and PK of lasmiditan in female subjects compared to male subjects.	AUC(0-∞), C max , and t max .

Abbreviations: AUC(0-∞) = area under the concentration versus time curve from time 0 extrapolated to infinity; Cmax = maximum observed plasma concentration; PK = pharmacokinetics; SAE = serious adverse event; TEAE = treatment-emergent adverse event; tmax = time of maximum observed plasma concentration.

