## 5.4. Scientific Rationale for Study Design

A subject- and investigator-blinded, randomized, and placebo-controlled design has been chosen to minimize bias in the primary objective of this study, and a crossover design has been chosen to minimize the number of subjects required for the study. The study design that has been chosen is considered to be the most feasible to execute operationally. As this will be the first time that the commercial formulation of lasmiditan will be administered to humans, Caucasian

subjects have been included to allow comparisons between Japanese and Caucasian subjects to be made.

Single and repeated doses (2 single doses administered 2 hours apart) of 50, 100, and 200 mg lasmiditan are considered the planned clinical doses. Additionally, a supratherapeutic dose of 400 mg lasmiditan has been included for the assessment of QT interval. As patients currently receiving approved therapies for migraine may administer an additional dose 2 hours following their initial dose if symptoms do not alleviate, this study will also evaluate the safety, tolerability, and PK of 2 doses of 200 mg lasmiditan administered 2 hours apart.

Pharmacokinetic sampling time points have been selected to generate PK profiles sufficient to fulfill the study objectives.

Conducting the study in healthy subjects mitigates the potential confounding effects of the disease state and concomitant medications in patients. Healthy subjects are frequently used in the assessment of bioavailability of both small and large molecules. Conducting this study in Japanese subjects will support their inclusion in future studies with lasmiditan, and inclusion of Caucasian subjects enables the direct comparison between Japanese and Caucasian subjects.

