5. STUDY DESIGN

This is a randomized, 3-period, subject- and investigator-blind, crossover study in healthy Japanese and Caucasian subjects.

Subjects will be evaluated for study eligibility ≤ 28 days prior to enrollment. Subjects who fulfil the eligibility criteria will be admitted to the clinical research unit (CRU) on Day -1 in Period 1 (the day before their first dose of lasmiditan or placebo).

Subjects will be enrolled into 1 of 3 cohorts. Within each cohort, subjects will be randomized to a treatment sequence, as indicated in Table 1, Table 2, and Table 3. Randomization will be stratified by sex, such there will be an approximately equal number of male and female subjects in each cohort.

Table 1. Treatment Sequences for Cohort 1; Japanese Subjects

Treatment Sequence	Period 1	Period 2	Period 3
1	Placebo	100 mg lasmiditan	200 mg lasmiditan
2	50 mg lasmiditan	Placebo	200 mg lasmiditan
3	50 mg lasmiditan	100 mg lasmiditan	Placebo

Table 2. Treatment Sequences for Cohort 2; Japanese Subjects

Treatment Sequence	Period 1	Period 2	Period 3 ^a
1	Placebo	400 mg lasmiditan	2 x 200 mg lasmiditan
2	50 mg lasmiditan	Placebo	2 x 200 mg lasmiditan
3	100 mg lasmiditan	400 mg lasmiditan	2 x placebo
4	200 mg lasmiditan	400 mg lasmiditan	2 x 200 mg lasmiditan

^a Doses administered 2 hours apart

Table 3. Treatment Sequences for Cohort 3; Caucasian Subjects

Treatment Sequence	Period 1	Period 2	Period 3
1	Placebo	100 mg lasmiditan	200 mg lasmiditan
2	50 mg lasmiditan	Placebo	200 mg lasmiditan
3	50 mg lasmiditan	100 mg lasmiditan	Placebo
4	50 mg lasmiditan	100 mg lasmiditan	200 mg lasmiditan

After randomization on Day 1, investigational medical product will be administered orally on the morning of Day 1 after an overnight fast of at least 8 hours. Blood samples will be collected for PK analysis predose, and for up to 48 hours postdose in each period. There will be a washout period of approximately 72 hours between dose administrations across periods.

Subjects will be discharged from the CRU following completion of all scheduled procedures on Day 3 of Period 3, as defined in the Schedule of Activities (Section 2 in the protocol), and will attend a follow-up visit 7 to 10 days following discharge from the CRU on Day 3 of Period 3.

Safety and tolerability will be assessed throughout the study by means of an adverse event (AE) review, physical examinations, body weight, vital sign measurements, 12-lead

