7. SAMPLE SIZE JUSTIFICATION

The sample size is customary for Phase 1 studies evaluating safety and PK, and is not powered on the basis of statistical hypothesis testing.

Subjects who are randomized but not administered treatment may be replaced to ensure that approximately 14 Japanese and 8 Caucasian subjects (approximately 2 per treatment sequence) may complete the study.

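### The pooled lasmiditan and placebo columns in the adverse event tables (SAP 9.4.1) cover unequal numbers of dosing periods, and different doses in the two populations

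*SAP*

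**What the plan says.** SAP section 9.4.1 says that the frequency "of treatment-emergent AEs will be summarized by treatment (including overall lasmiditan treatment periods and overall placebo treatment periods"). Frequency there includes "the number of subjects experiencing an AE and the percentage of subjects experiencing an AE", so the percentage is of subjects with any event, not of periods. The tables are split by population and by sex within population; one is titled "Frequency of Subjects with Treatment-Emergent AE (All Causalities) by Population".

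On the design, SAP section 5 states: "Within each cohort, subjects will be randomized to a treatment sequence, as indicated in Table 1, Table 2, and Table 3". SAP section 7 plans replacement so that "approximately 14 Japanese and 8 Caucasian subjects (approximately 2 per treatment sequence) may complete the study".

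The primary endpoint in protocol Table LAIE.4.1 is "Incidence of TEAEs and SAEs". Protocol section 5.4 says that a "placebo-controlled design has been chosen to minimize bias in the primary objective of this study". Protocol section 3.1 adds: "Caucasian subjects are included to explore the differences in safety, tolerability, and PK of lasmiditan between Japanese and Caucasian subjects".

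For the two pooled columns, SAP section 9.4.1 gives no denominator rule, no count of periods, no per-period rate and no caution. SAP section 3 leaves table detail to a separate shell document, which is not available here. SAP section 9.4.9 plans no inferential safety analysis.

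**The concern.** The percentage of subjects with at least one event grows with the number of periods in which an event can occur. In a single-treatment column each recipient contributes one period, so this does no harm. In the pooled columns, two or three lasmiditan periods per subject stand beside at most one placebo period. The pooled lasmiditan figure can then exceed the pooled placebo figure with no drug effect.

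The lasmiditan pool also has one label in both populations but different contents: 400 mg and 2 x 200 mg are given only in Cohort 2, which is Japanese. If adverse events rise with dose, the Japanese pool can look worse with no difference between populations.

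These are the two contrasts, drug against placebo and Japanese against Caucasian, that the protocol gives as reasons for its design. A reader in a hurry is likely to look for them in the overall columns.

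**Working it through.** **Inputs.** Sequences: SAP section 5, Tables 1-3. Completers: SAP section 7. The documents give no event risk, within-subject correlation or dose-response size, so those below are assumptions. The pooled denominator is taken to be subjects given at least one dose of that pooled treatment.

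**Planned numbers reproduced.** Japanese: 7 sequences x 2 = 14. Caucasian: 4 x 2 = 8. Both agree with SAP section 7.

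**Period counts at 2 per sequence.**

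| | Japanese | Caucasian |
|---|---|---|
| Subjects with 2 / 3 lasmiditan periods | 12 / 2 | 6 / 2 |
| Lasmiditan periods | 12x2 + 2x3 = 30 | 6x2 + 2x3 = 18 |
| Subjects with 1 / 0 placebo periods | 12 / 2 | 6 / 2 |
| Placebo periods | 12 | 6 |
| Lasmiditan periods by treatment | 6 each of 50, 100, 200, 400 and 2 x 200 mg | 6 each of 50, 100 and 200 mg |
| Periods totalling 400 mg | 12 of 30 (40%) | 0 of 18 |
| Mean total dose per period | (50+100+200+400+400)/5 = 230 mg | (50+100+200)/3 = 117 mg |

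**Unequal periods, no drug effect.** Let p be the risk per period, the same on drug and placebo.

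- Independent periods: P(any event in k periods) = 1 - (1-p)^k. At p = 0.20 this is 0.360 for k = 2 and 0.488 for k = 3. Japanese: (12x0.360 + 2x0.488)/14 = 0.378. Caucasian: (6x0.360 + 2x0.488)/8 = 0.392.
- Correlation 0.5 (beta-binomial with parameters 0.2 and 0.8): P(none in 2) = 0.8 x 1.8/2 = 0.720 and P(none in 3) = 0.720 x 2.8/3 = 0.672, so P(any) is 0.280 and 0.328. Japanese: (12x0.280 + 2x0.328)/14 = 0.287. Caucasian: (6x0.280 + 2x0.328)/8 = 0.292.
- Perfect correlation: 0.20 in both.

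The same formulas at other risks give:

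| Risk per period = pooled placebo | Pooled lasmiditan, correlation 0.5 (Japanese / Caucasian) | Pooled lasmiditan, independent (Japanese / Caucasian) |
|---|---|---|
| 10% | 14.9% / 15.2% | 20.2% / 21.0% |
| 20% | 28.7% / 29.2% | 37.8% / 39.2% |
| 30% | 41.4% / 42.0% | 53.1% / 54.7% |

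**Dose mix, no population effect.** Assume 20% risk at 50-200 mg and 40% at 400 mg total in both populations.

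- Independent periods. The 6 Cohort 1 subjects have 0.36 each. Cohort 2 sequences 1 to 4 have 1 - 0.6x0.6 = 0.64, 1 - 0.8x0.6 = 0.52, 0.52 and 1 - 0.8x0.6x0.6 = 0.712. Japanese: [6x0.36 + 2x(0.64+0.52+0.52+0.712)]/14 = 0.496. Caucasian: 0.392. With 30% or 50% at 400 mg total, Japanese becomes 0.440 or 0.547.
- Fully dependent periods (a subject who reacts at a lower dose also reacts at 400 mg). 8 of the 14 Japanese subjects have at least one 400 mg-total period: (6x0.20 + 8x0.40)/14 = 0.314, against 0.20 in Caucasian subjects.

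The gap is 10 to 11 points in either case, so it does not rest on independence.

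**Shared-dose pool.** The 50, 100 and 200 mg single-dose periods number 18 in each population. In Japanese subjects they come from 12 subjects: 6 with two periods (Cohort 1) and 6 with one (Cohort 2, sequences 2-4). In Caucasian subjects they come from 8: 6 with two and 2 with three. A subject percentage in this pool would again be uneven, at 20% and independence (6x0.36 + 6x0.20)/12 = 0.28 against 0.392. A rate per period would be 0.20 in both.

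**The case against.** Much of the case on the other side stands.

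- **The primary endpoint does not depend on these columns.** Protocol section 10.3.1.1 presents incidence for each treatment, SAP section 6 lists seven treatments with no pooled entry, and the overall columns are an addition in parentheses. The by-treatment columns give sound incidence, and at 50, 100 and 200 mg they already allow a comparison across populations.
- **No pooled comparison is planned.** Neither document says that overall lasmiditan will be compared with overall placebo, or one population's pool with the other's. The misreading needs a reader to do this unprompted and pass over the adjacent dose columns.
- **The table shells are unseen.** They may define denominators or carry footnotes. One can say only that SAP section 9.4.1 is silent.
- **The sizes are assumed.** Periods in one subject are unlikely to be independent, so 38-39% is toward the upper end for that risk. On dose-response the protocol points both ways: section 3.3 says nervous system events were common especially at higher doses, while section 3.2 calls tolerability in healthy subjects similar up to 400 mg.
- **The pharmacokinetic section is no precedent.** SAP section 9.3.2 fits dose proportionality within each population over that population's own range. It does not restrict Japanese data to the shared doses.

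What remains is the structure. The pattern of two or three lasmiditan periods against one or no placebo periods comes from the sequences and holds whatever the enrolment. Naming the columns by treatment periods tells the reader what was pooled, but the reported percentage is still of subjects. The listings would let someone rebuild a per-period rate, but the tables would not show it.

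**Conclusion.** The pooled subject percentages are not like for like. Lasmiditan has 30 periods against 12 on placebo in Japanese subjects, and 18 against 6 in Caucasian subjects. With equal risk per period, pooled lasmiditan would exceed pooled placebo unless events are perfectly correlated within subject: by nothing at that limit, by about 9 points at correlation 0.5 and by 18 to 19 points under independence, at an assumed 20% risk. The dose content also differs by population, which matters only if events rise with dose.

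A reader might infer that the primary endpoint analysis is biased, or that the trial cannot compare drug with placebo or Japanese with Caucasian subjects. The documents do not support that: the incidence by treatment is unaffected, the safety analysis is descriptive, and no conclusion is tied to the pooled columns. Nor do they show that the final tables will lack a denominator or caution, since the shells are not available.

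The period counts assume 2 completers per sequence. Severity: minor, an optional improvement.

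**What to change.** In SAP section 9.4.1:

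1. For the overall lasmiditan and overall placebo columns, show the number of periods dosed, and report periods with a treatment-emergent event over periods dosed beside the subject percentage. The planned denominators are 30 and 12 (Japanese) and 18 and 6 (Caucasian).
2. For reading across populations, add or substitute a pool limited to the shared 50, 100 and 200 mg single-dose periods, 18 planned in each population. Read it by the rate per period, because those periods are spread over 12 Japanese but 8 Caucasian subjects.
3. Footnote the pooled columns: the subject percentages cover unequal numbers of periods and, between populations, different doses.

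The by-treatment columns need no change. The cost is a few sentences in the SAP, an extra row or column and a footnote in the adverse event tables. The subject count stays. No new data are needed, because SAP section 9.4.8 already lists dosing details for each subject.

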9.4.2 Concomitant medication

Concomitant medication will be coded using the WHO drug dictionary (Version March 2018 Enhanced B2). Concomitant medication will be listed.

9.4.3 Clinical laboratory parameters

All clinical chemistry and hematology data will be summarized by population, parameter, and treatment, and listed. Urinalysis data will be listed. Additionally clinical chemistry, hematology and urinalysis data outside the reference ranges will be listed.

Values for any clinical chemistry, hematology and urinalysis values outside the reference ranges will be flagged on the individual subject data listings.

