## 2. Schedule of Activities

## Study Schedule Protocol H8H-JE-LAIE

	Screening	Period 1			Period 2			Period 3			Follow-up/ED	Comments
		Day										
Procedure	-28 to -2 days prior to Day 1 of Period 1	-1	1	2	3	1	2	3	1	2	3	7 to 10 days following Day 3 of Period 3
Informed Consent	X											
Subject Admission to CRU		X										
Subject Discharge from CRU										X		
Chest X-ray	X											
Enrollment/ Randomization		X										
Lasmiditan Administration		X			X			X a				A washout of approximately 72 hours between doses across periods
Medical History	X	X										Interim medical history only on Day -1
Urine Drug Screen	X	X										
Alcohol Test		X										
Height	X											
Body Weight	X	X									X	
Triplicate Vital Signs (supine)	X	-1, -0.5, P, 0.5, 1, 1.5, 2, 2.5, 3, 4, 6, 8, 12	24, 36	48	P, 0.5, 1, 1.5, 2, 2.5, 3, 4, 6, 8, 12	24, 36	48	P, 0.5, 1, 1.5, 2, 2.5, 3, 3.5 b , 4, 4.5 b , 5 b , 6, 8, 12	24, 36	48	X	Time points relative to the time of investigational product administration in each period and shown in hours. For repeated doses, timepoints relative to the first dose. Single vital signs only at follow-up/ED. Time points may be added, if warranted and agreed by Lilly and the investigator
Single Orthostatic Vital Signs	X	-1, P, 1, 2, 3, 4, 6, 8, 12	24, 36	48	P, 1, 2, 3, 4, 6, 8, 12	24, 36	48	P, 1, 2, 3, 4, 6, 8, 12	24, 36	48	X	Time points relative to the time of investigational product administration in each period. For repeated doses, time points relative to the first dose. Time points may be added if warranted and agreed by Lilly and the investigator
Clinical Laboratory Tests	X	P			P			P			X	See Appendix 2 , Clinical Laboratory Tests, for details

	Screening	Period 1			Period 2			Period 3			Follow-up/ED	Comments	
		Day											
Procedure	-28 to -2 days prior to Day 1 of Period 1	-1	1	2	3	1	2	3	1	2	3	7 to 10 days following Day 3 of Period 3	
Adverse Event Review	X	X	X	X	X	X	X	X	X	X	X	X	
Pregnancy Test	X	X									X	Serum pregnancy test for all females	
Follicle-stimulating hormone	X												Postmenopausal females only
Physical Examination	X	X			X			X			X	X	Full physical examination performed at screening. At other time points, symptom-directed physical examination only

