Triplectate 12-lead Electrocardiogram	X	-1, -0.5, P, 1, 1.5, 2, 2.5, 3, 4, 6, 8, 12	24, 36	48	P, 1, 1.5, 2, 2.5, 3, 4, 6, 8, 12	24, 36	48	P, 1, 1.5, 2, 2.5, 3, 4, 6, 8, 12	24, 36	48	X	Time points relative to the time of investigational product administration in each period. For repeated doses, time points relative to the first dose. Refer to Section 9.4.4. Performed after subject has rested in supine position for ~5 to 10 minutes. On days without dosing, should be performed close to the Day 1 dosing time, when possible. Collected in triplicate except at screening and follow-up/ED	
Columbia-Suicide Severity Rating Scale/Self-Harm	X	X									X	X	
Genetic Sample			X										Period 1 only
Blood Sample for Lasmiditan and Metabolites Pharmacokinetics		P, 0.5, 1, 1.5, 2, 2.5, 3, 4, 6, 8, 12	24, 36	48	P, 0.5, 1, 1.5, 2, 2.5, 3, 4, 6, 8, 12	24, 36	48	P, 0.5, 1, 1.5, 2 c , 2.5, 3, 3.5 b , 4, 4.5 b , 5 b , 6, 8, 12	24, 36	48			Time points relative to the time of investigational product administration in each period. For repeated doses, time points relative to the first dose

Abbreviations: CRU = clinical research unit; ED = early discontinuation; P = predose.

Note: if multiple procedures take place at the same time point, the following order of the procedure should be use: electrocardiogram, vital signs, and venipuncture.

- a Subjects in Period 3 of Cohort 2 will receive 2 doses separated by 2 hours.
- b Subjects in Period 3 of Cohort 2 only.
- c For subjects in Period 3 of Cohort 2, pharmacokinetic sample collected prior to second dose.

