#### 3.2. Background

Lasmiditan has a chemical structure and pharmacological profile that is distinct from triptans, which are the current standard of care for the treatment of acute migraine. It does not contain the indole group found in all triptans, but instead has a pyridinoyl-piperidine scaffold that is unique to antimigraine medications. Lasmiditan is a low-molecular weight agonist of the 5-HT1F receptor with a nonvascular and primarily neural mechanism of action. It has a high affinity for the human 5-HT1F receptor and a >470-fold selectivity for the human 5-HT1F receptor relative to the 5-HT1B receptor.

Lasmiditan doses of 0.1 to 400 mg have been evaluated in healthy subjects or patients with migraine across completed Phase 1, 2, and 3 clinical studies. The most frequently reported lasmiditan treatment-emergent adverse events (TEAEs) in the two Phase 3, placebo-controlled studies in which patients treated 1 migraine attack with oral lasmiditan (50, 100, or 200 mg) or placebo were dizziness, paresthesia, somnolence, fatigue, lethargy, and nausea, and the majority were mild or moderate in severity. Safety and tolerability in healthy subjects were similar up to 400 mg, with tiredness, drowsiness, dizziness, and paresthesia being the most frequently reported adverse events (AEs). The majority of these were mild in severity, and none were severe. In healthy subjects, peak plasma concentrations of lasmiditan were observed approximately 1.5 to 2.5 hours after a single oral dose ranging from 25 to 400 mg, and the geometric mean terminal half-life was approximately 4 hours. Lasmiditan PK was approximately dose linear. There was an increase of approximately 20% to 30% in maximum observed plasma concentration (Cmax) and a 30% increase in area under the concentration versus time curve (AUC) in female subjects in a previous study.

Following oral dosing with lasmiditan, up to 16 metabolites, including 3 major metabolites (M7, M8, and M18), were detected in human plasma and urine. These metabolites lacked significant pharmacological activity at the 5 HT1F receptor and were generally considered to be pharmacologically inactive. The relative proportions of metabolites to intact lasmiditan remained reasonably constant throughout the oral dose range studied and their PK was approximately linear. The half-life of the metabolites ranged from approximately 4.5 to 21 hours.

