**Table LAIE.5.3. Treatment Sequences for Cohort 2; Japanese Subjects**

Treatment Sequence	Period 1	Period 2	Period 3 a
1	Placebo	400 mg lasmiditan	2 $\times$ 200 mg lasmiditan
2	50 mg lasmiditan	Placebo	2 $\times$ 200 mg lasmiditan
3	100 mg lasmiditan	400 mg lasmiditan	2 $\times$ placebo
4	200 mg lasmiditan	400 mg lasmiditan	2 $\times$ 200 mg lasmiditan

a Doses administered 2 hours apart.

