**Table LAIE.5.4. Treatment Sequences for Cohort 3; Caucasian Subjects**

Treatment Sequence	Period 1	Period 2	Period 3
1	Placebo	100 mg lasmiditan	200 mg lasmiditan
2	50 mg lasmiditan	Placebo	200 mg lasmiditan
3	50 mg lasmiditan	100 mg lasmiditan	Placebo
4	50 mg lasmiditan	100 mg lasmiditan	200 mg lasmiditan

After randomization on Day 1, investigational medical product will be administered orally on the morning of Day 1 after an overnight fast of at least 8 hours. Blood samples will be collected for PK analysis predose, and for up to 48 hours postdose in each period. There will be a washout period of approximately 72 hours between dose administrations across periods.

Subjects will be discharged from the CRU following completion of all scheduled procedures on Day 3 of Period 3, as defined in the Schedule of Activities (Section 2), and will attend a follow-up visit 7 to 10 days following discharge from the CRU on Day 3 of Period 3.

Safety and tolerability will be assessed throughout the study by means of AE review, physical examinations, body weight, vital sign measurements, 12-lead electrocardiograms (ECGs), clinical laboratory tests, and Columbia-Suicide Severity Rating Scale (C-SSRS).

Details for the timing of dosing are presented in Section 10.3.3.

Study governance considerations are described in detail in Appendix 3.

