#### **10.3.1.2. Statistical Evaluation of Safety**

Safety parameters that will be assessed include body weight, vital sign measurements, ECG parameters, clinical laboratory tests, and C-SSRS. The parameters will be listed, and summarized using standard descriptive statistics. Additional analysis will be performed if warranted upon review of the data.

Prior to any statistical analysis of QT interval, QT values will be corrected for heart rate (corrected QT interval based on Fridericia's formula [QTcF]). The relationship between concentrations of lasmiditan and changes from baseline QTcF ( $\Delta$ QTcF) will be explored to assess the effect of lasmiditan concentration on the  $\Delta$ QTcF. A detailed analysis for QT interval will be provided in the statistical analysis plan. Additional analysis will be performed if warranted upon review of the data.

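### Do the by-treatment laboratory tables need a stated time point and attribution rule, given that every scheduled in-period sample is predose?

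*SAP*

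**What the plan says.** The whole summary rule for laboratory data in SAP 9.4.3 is: "All clinical chemistry and hematology data will be summarized by population, parameter, and treatment, and listed". Urinalysis is listed only. Values outside the reference ranges are flagged in the listings and also listed separately. The section gives no time point, no baseline, and no statement of which treatment a sample belongs to.

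In the protocol's Schedule of Activities, the row "Clinical Laboratory Tests" has a sample at screening, one marked P in each of Periods 1, 2 and 3, and one at follow-up or early discontinuation. The footnote defines P: "Abbreviations: CRU = clinical research unit; ED = early discontinuation; P = predose". Follow-up is timed "7 to 10 days following Day 3 of Period 3". On spacing, protocol 5.1 says: "There will be a washout period of approximately 72 hours between dose administrations across periods".

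Protocol 10.3.1.2 names clinical laboratory tests among the safety parameters and promises only this: "The parameters will be listed, and summarized using standard descriptive statistics".

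SAP 3 says the planned tables are described in detail in an accompanying shell document. SAP 6 gives seven treatment labels and keeps placebo and 2 x placebo apart.

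**The concern.** A table headed by treatment is normally read as showing values under that treatment. Here every scheduled in-period sample comes before the dose of its own period. If samples are filed by period, the column label names a treatment the subject has not yet had when the blood is drawn.

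The 400 mg dose looks like the sharpest case. It is the highest single dose in the first Japanese exposure. It is given only in Period 2 of Cohort 2 (table headed "Treatment Sequences for Cohort 2; Japanese Subjects") and is always followed by a Period 3 treatment. Its next scheduled sample would be filed under 2 x 200 mg or 2 x placebo, so a persisting laboratory shift could appear under the wrong label, even a placebo label. Safety is the primary objective, so the question deserves a check.

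**Working it through.** **Number of samples.** After screening the schedule has three predose samples and one at follow-up: 3 + 1 = 4. Protocol Appendix 5 gives 4 samples of 12.5 mL, and 4 × 12.5 = 50 mL, as stated there. No further scheduled in-period sample exists.

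**Counts.** Inputs are the sequence tables in protocol 5.1 (7 Japanese and 4 Caucasian sequences) and 2 completers per sequence (protocol 5.2). That gives 14 + 8 = 22 subjects and 22 × 3 = 66 predose samples. Two filing rules are compared: own period, and last treatment received. Follow-up falls in the same column under both rules, provided own-period filing places it with Period 3.

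| Column | Predose values, own-period filing | About-72 h values, last-treatment filing | Follow-up values, either filing |
|---|---|---|---|
| Japanese placebo | 10 | 8 | 2 |
| Japanese 2 x placebo | 2 | 0 | 2 |
| Japanese 50 mg | 6 | 6 | 0 |
| Japanese 100 mg | 6 | 6 | 0 |
| Japanese 200 mg | 6 | 2 | 4 |
| Japanese 400 mg | 6 | 6 | 0 |
| Japanese 2 x 200 mg | 6 | 0 | 6 |
| Caucasian placebo | 6 | 4 | 2 |
| Caucasian 50 mg | 6 | 6 | 0 |
| Caucasian 100 mg | 6 | 6 | 0 |
| Caucasian 200 mg | 6 | 0 | 6 |
| Total | 66 | 44 | 22 |

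The 44 are the Period 2 and 3 predose samples (22 × 2). The other 22 predose samples, from Period 1, precede all treatment.

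**The 400 mg column.** Under own-period filing its 6 values follow placebo (2), 100 mg (2) and 200 mg (2). The 6 samples drawn about 72 hours after 400 mg fall under 2 x 200 mg (4) and 2 x placebo (2).

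**Is 400 mg special?** No. The 50 mg and 100 mg columns also have no postdose value under own-period filing, in either population. The same holds for the 2 Japanese subjects given 200 mg in Period 1. Only Period 3 treatments receive a scheduled postdose value, from follow-up. This is a general labelling matter, not a gap at the top dose.

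**What the samples can show.** Protocol 3.2 says "the geometric mean terminal half-life was approximately 4 hours", so the about-72 h samples come 72 / 4 = 18 half-lives of parent lasmiditan after dosing. For the metabolites, with half-lives of about 4.5 to 21 hours, the range is 72 / 21 = 3.4 to 72 / 4.5 = 16. Day 3 is 2 days after dosing, so follow-up comes 2 + 7 = 9 to 2 + 10 = 12 days after the Period 3 dose. Under any filing rule these samples detect persisting changes, not effects near peak concentration.

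**Does the silence mean time points will be pooled?** SAP 9.4.4 and 9.4.5 use the same shorthand: their summary sentences name population and treatment but no time point, although those data run to more than ten time points per period. SAP 9.4.3 covers all chemistry and hematology data, which includes screening and follow-up. A screening value has no treatment, so the table needs some visit or time-point dimension anyway. With that printed, a Period 2 predose value under 400 mg is correctly labelled as the value before 400 mg.

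**The case for a change.** The best case for a change is that the SAP supplied such a rule elsewhere. Sections 9.4.4 and 9.4.5 define a baseline and treat Period 2 and 3 predose values as post baseline, and SAP version 2 clarified exactly those two sections. Laboratory data, where every in-period sample is predose, got nothing. Printing the time point does not move the six post-400 mg samples to the 400 mg column. One sentence would, taking that column from 0 to 6 postdose values at no cost in data collection.

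The omission and the counts stand. The step from there to a needed change does not. Own-period filing is an inference, since the SAP does not state it and the shells could not be checked. Filing by last treatment is also only a convention. It sends follow-up samples of subjects in Cohort 2 sequence 3 to 2 x placebo, one period after 400 mg, and those of sequence 3 in Cohorts 1 and 3 to placebo, one period after 100 mg. It leaves 2 x 200 mg, Caucasian 200 mg and 4 of the 6 Japanese 200 mg subjects with follow-up samples only. Earlier exposure is relabelled, not removed.

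**Conclusion.** No change is needed. This is missing table detail of the kind that shells and analysts settle sensibly, and the protocol's promise of listings and descriptive summaries is met as worded.

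The effect is confined to column placement in descriptive chemistry and hematology tables: at most 44 predose samples from Periods 2 and 3, among them 6 drawn about 72 hours after 400 mg. Every value is listed by subject and out-of-range values are flagged. Adverse events, which by the protocol's definition can include abnormal laboratory findings, are tabulated separately under SAP 9.4.1. Hepatic monitoring has its own triggers. The investigator must document review of each laboratory report (protocol 9.2), and the sponsor's physician periodically reviews laboratory analytes (protocol 9.4.6). SAP 9.4.9 plans no inferential safety analysis that a labelling choice could bias.

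The counts assume 2 completers per sequence and scheduled samples only. An early discontinuation or unscheduled sample could still put a post-400 mg value in the 400 mg column. The conclusion also assumes that the tables distinguish time points. If they pooled all samples in a treatment column without a time label, the summaries would be poorly labelled, but the listings and flags would still carry the safety information.
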